6.4 Study Assessments

(ICH E3; 9.5.1. ICH E9; 2.2.2)

Visit Description	Patient Eligibility Screen and Enrollment	Randomization		Discharge	Follow-up Period	
Study visit: Study Day (Range of assessment periods)	Visit 1: Day 0 (+/- 14 days)	Visit 2: Day 7 (-2, +8 days)	Treatm ent Period ¹	Visit 3: Day² (-14, +30 days)	Visit 4: 180 Days after Discharge (6 month) (-30, +60 days)	Visit 5: 360 Days after Discharge (12 month) (-30, +60 days)
Informed Consent/HIPAA	х					
Demographics/ Medical History	x					
Accelerometer	Х			Х	Х	Х
Randomization		Х				
Adverse Events			Х	Х	Х	Х
 1 – Study intervention will be delivered when the study participant visit PT. The total number of visits will be based on the number of PT visits during the PT episode of care. The number of visits will be based clinically on physical therapist discretion in accordance with standard physical therapy guidelines. 2 – The study visit day varies depending on the duration of outpatient PT 						

Data collected outside of the time windows listed above will be classified as the intended visit the data was to reflect and noted as being outside the time window. Such data will be included in the primary analyses, however we will also perform a secondary analyses excluding data collected outside the time window.

Study Variable	Description	Endpoints	Interpretation	
Age	Age of study participant in years	Minimum 45 years	N/A	
Gender	Self-reported Sex of study participant	Male/Female	N/A	
BMI	Body Mass Index calculated from weight and height.	Body Mass Index calculated from weight and beight		
Race	Self-reported race	Self-reported race White, Black or African American, Asian, American Indian or Alaskan Native, Hawaiian, more than one race, other		
Hispanic	"Do you consider yourself to be Hispanic or Latino?"	Yes/No	N/A	
Health History Questionnaire	The number of comorbidities from a list of 54 possible conditions	N/A	N/A	
Moderate to Vigorous intensity Physical Activity (MVPA)	MVPA calculated from a monitor (ActiGraph GT3x)	Continuous measure. Minimum value 0 minutes/day	Higher values indicate greater time in MVPA	
Steps/Day	Steps/day calculated from a monitor (ActiGraph GT3x)	Continuous measure. Minimum value 0 steps/day	Higher values indicate greater steps taken/day	
Adverse Event	Defined as any unfavorable or unintended diagnosis, sign, symptom, or disease that is associated with the study and that may or may not be related to the intervention.	Continuous number of adverse events	N/A	

7 Sample Size

(ICH E3; 9.7.2. ICH E9; 3.5) The sample size was N=120 study participants.

General Analysis Considerations

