#### 7. STUDY POPULATION AND RECRUITMENT

Describe who and how many subjects will be invited to participate. Include age, gender and other pertinent information.

The enrollment capacity for this protocol is 173 participants. This includes two projects:

- 1. 43 participants enrolled in the pilot phase of this study (9/26/16 6/27/17)
- 2. 130 participants targeted enrollement for the current study (6/28/17 ongoing)

Inclusion:

- Participants over the age of 45
- Seeking outpatient physical therapy rehabilitation for a unilateral TKR

Note: Participants are included irrespective of time since surgery as long as they are seeking PT for a unilateral TKR

Exclusion:

- No interest in increasing physical activity
- Having had another lower extremity surgery within 6-months that is unrelated to the TKR
- Planning on having another lower extremity surgery within 6-months that is unrelated to the TKR

• Any other medical condition that limits the participant's ability to participate in physical activity.

Examples of medical conditions that limit physical activity include but are not limited to the following:

- 1. Epilepsy
- 2. Parkinson's disease
- 3. Neuropathy
- 4. Dementia
- 5. Require the use of a wheelchair
- 6. Rheumatoid arthritis
- 7. Psychiatric disease
- 8. Alcohol and/or drug abuse
- 9. Current cancer treatment
- 10. Uncontrolled diabetes (glycosylated hemoglobin level >7.0)
- 11. Neurologic, vascular or cardiac problems that limit physical activity
- 12. Orthopedic conditions that limit physical activity such as lumbar stenosis, severe hip or ankle OA
- Previous enrollment in a physical activity intervention study at the University of Delaware Physical Therapy clinic

Note: Participants are not excluded based on smart device usage and/or access to internet

Describe what (if any) conditions will result in PI termination of subject participation.

Discontinuation from the physical activity intervention does not mean discontinuation from the study, and remaining study procedures should be completed as indicated by the study protocol. If a clinically significant finding is identified (including, but not limited to changes from baseline) after enrollment, the principal investigator or qualified designee will determine if any change in participant management is needed. Any new clinically relevant finding will be reported as an adverse event (AE).

An investigator may discontinue or withdraw a participant from the intervention for the following reasons:

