6.3 Randomization and Blinding

(ICH E3; 9.4.3, 9.4.6. ICH E9; 2.3.1, 2.3.2)

Participant-level randomization was performed to assign each participant to either the Intervention group or the Control group using a simple randomization schedule from the RAND() function in Microsoft Excel. Randomization occurred after participants provided signed informed consent to participate in the study and a research assistant determined they met study criteria. Randomization could have occurred after study participants started standardized outpatient PT.

A researcher not involved in recruitment or outcome assessment accessed the schedule, informed participants of their group assignment, and group assignment was concealed from the remaining members of the research team. This included blinding all members of the research team who were involved in the assessment of primary and secondary outcomes, or in statistical analysis of study outcomes. Participants and treating PTs were not blinded to their group assignment.

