7.3 Covariates and Subgroups

(ICH E3; 9.7.1, 11.4.2.1. ICH E9; 5.7)

We have identified three covariates that are expected to have an important influence on our study outcomes, i.e., age, sex, and body mass index. We will adjust for these covariates in all analyses. In particular, age and body mass index will be treated as continuous variables, and sex as a categorical variable. We will perform separate subgroup analyses to examine evidence for a difference in treatment effects based on 1) Age (< and \geq 65 years), 2) Sex (men and women), and 3) BMI (< and \geq 32 kg/m2).

SAP version 1.0: Physical Activity Intervention after TKR 3/16/23

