8.2 Demographic and Baseline Variables

Characteristic [mean ± SD or n (%)]	All n=	Intervention n=	Control n =
Age (years)			
Gender (female)			
BMI (kg/m²)			
Race (Non-White)			

Comorbidity (Health History Questionnaire)		
MVPA at baseline (minutes/day)		
Steps/day at baseline		
Days between TKR and PT Evaluation		

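### Time since surgery at entry is recorded but left out of the models for change in MVPA, which costs some precision and control of chance imbalance, not validity

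*SAP*

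**What the plan says.** **Entry.** Protocol section 7 states: "Participants are included irrespective of time since surgery". SAP 6.3 describes simple randomisation, with no stratification, and allows it to occur after PT has begun.

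**Visit clock.** SAP 6.4 times the 6- and 12-month visits from PT discharge. Of the discharge visit it says: "The study visit day varies depending on the duration of outpatient PT". It adds: "The number of visits will be based clinically on physical therapist discretion in accordance with standard physical therapy guidelines". SAP 6.3 states: "Participants and treating PTs were not blinded to their group assignment". SAP 7.4, by contrast, describes the four measurement times as fixed.

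**Models.** SAP 9 frames the null hypothesis as no difference between groups in change in MVPA. SAP 9.1 fits group, nominal visit (baseline, discharge, 6 months) and their interaction. SAP 7.3 names "three covariates that are expected to have an important influence on our study outcomes": age, sex and BMI. No other adjustment is planned in any model.

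**Timing variables.** "Days between TKR and PT Evaluation" is a row of the baseline table (SAP 8.2). Days from evaluation to discharge and from randomisation to discharge are summarised by arm (SAP 8.3). None of these enters a model.

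**The concern.** Two separate matters arise.

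The first is before randomisation. If entry is open to any time since surgery, some baseline recordings fall early in recovery and others late. An early baseline is likely to be low and to leave more room for change. That adds spread to the change score, and simple randomisation lets the arms differ by chance in time since surgery. Protocol section 6 gives a limited hint that this matters: intervention participants less than three weeks after surgery are not expected to raise their step count. That rule concerns early step goals only. It is not evidence about MVPA months after discharge.

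The second is after randomisation. The 6-month clock starts at discharge, which follows randomisation and depends partly on therapists who know the arm. If PT length differed by arm, the 6-month label would stand for different elapsed times in the two arms. The planned analysis excluding out-of-window data (SAP 6.4) would not show this, because its follow-up windows are themselves counted from discharge.

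At stake are a modest amount of precision, protection against an unlucky allocation, and a direct check on timing.

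**Working it through.** **Inputs from the documents.** N = 120 (SAP 7); 6-month visit at day 180 after discharge, window -30 to +60 (SAP 6.4). The SAP gives no effect size, SD, power or allocation ratio, so N = 120 cannot be reproduced.

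**Assumed inputs.** 1:1 allocation (60 per arm); MVPA SD 15 min/day at each visit; correlation ρ = 0.4 between baseline and 6 months; complete data. Let r0 and r6 be the correlations of days since surgery with MVPA at baseline and at 6 months.

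**1. A main effect alone does nothing for change.** A baseline covariate with a single coefficient β moves the group difference at every visit by β × (arm imbalance in the covariate). The same amount is subtracted at baseline and at 6 months, so the change contrast is unaltered. Its SE is

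15 × √[2(1 − 0.4) × 2/60] = 15 × √0.04 = 3.00, with or without the covariate.

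Only the single-visit difference gains. Its SE is 15 × √(2/60) = 2.74, becoming 2.74 × √(1 − 0.2²) = 2.68 at r = 0.2 and 2.74 × √(1 − 0.3²) = 2.61 at r = 0.3.

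**2. With a covariate-by-visit interaction.** The residual variance of change falls by 15² × (r6 − r0)²:

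SE = 15 × √{[2(1 − ρ) − (r6 − r0)²] × 2/60}

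| r0 | r6 | SE of change contrast |
|---|---|---|
| 0.3 | 0.3 | 15 × √(1.20/30) = 3.00 |
| 0.3 | 0 | 15 × √(1.11/30) = 2.89 |

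The second row is a 7.5% reduction in variance (0.09/1.20).

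**3. Chance imbalance.** The arm difference in days since surgery has SE 2/√120 = 0.18 SD, so a 95% range of about ±0.36 SD. With r0 = 0.3 and r6 = 0, the change score moves 0.3 × 15 = 4.5 min/day per SD of the covariate. An allocation at the edge of that range would therefore shift the unadjusted change contrast by about 0.36 × 4.5 = 1.6 min/day in either direction, roughly half of its SE.

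**4. Timing.** The 6-month window runs from day 150 to day 240 after discharge, which is 90 days wide before any difference in PT length. If mean PT length did differ by arm, the shift would be (MVPA slope per 30 days) × (difference in days)/30, with both inputs assumed:

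| Slope (min/day per 30 days) | 7 days | 14 days | 28 days |
|---|---|---|---|
| 0.5 | 0.12 | 0.23 | 0.47 |
| 1 | 0.23 | 0.47 | 0.93 |
| 2 | 0.47 | 0.93 | 1.87 |

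With shift b, type I error for the single-visit difference is Φ(−1.96 + b/2.74) + Φ(−1.96 − b/2.74). A nominal two-sided 0.05 becomes 0.053 (slope 1, 14 days), 0.063 (slope 2, 14 days) or 0.105 (slope 2, 28 days).

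**The case against.** **Discharge timing is the endpoint, not an oversight.** SAP 5.2 and 9.1 define the primary question as MVPA over the 6 months after discharge, and SAP 6.1 calls the trial pragmatic. If the intervention altered PT length, activity six months after discharge would still answer that question. The shifts in step 4 count as bias only against a different, elapsed-time question. This stands, and it is why the discharge-anchored visits should remain primary.

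**No timing difference is shown.** A reader might infer that unblinded therapists setting discharge has biased the comparison. The documents do not support that. Discretion is bounded by standard guidelines, both arms receive PT under the same written rehabilitation guidelines (Protocol section 6), and PT length is tabulated by arm, so a difference would be visible. The documents' premise that patients tend to remain inactive after surgery also argues against a steep MVPA slope six months after discharge. What remains is a possibility that no planned analysis tests.

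**Three covariates were prespecified, and leaving out a fourth does not invalidate a randomised comparison.** This is correct. The case for adding this one is efficiency and protection against chance imbalance, and it depends on the covariate relating differently to baseline and to later MVPA.

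**Conclusion.** The point holds as a minor improvement. With entry unrestricted by time since surgery, simple randomisation and a hypothesis about change, leaving out a recorded pre-randomisation variable gives up some precision and some control over chance imbalance. It does not make the primary comparison invalid.

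On the assumptions above, the gain in SE for the change contrast ranges from nothing (equal correlation at all visits) to 3.00 down to 2.89 (0.3 at baseline, 0 at 6 months). A reader might apply the usual formula, 120/(1 − r²) − 120, and infer a saving of 5 participants at r = 0.2 or 12 at r = 0.3. That applies to a single-visit difference, not to the change contrast that the SAP tests, and should not be used for it.

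Timing bias remains only a possibility. The SD, correlations, slopes and PT-length differences used here are all assumed.

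**What to change.** 1. Add days from surgery to baseline, with its interaction with visit, to all MVPA and steps/day models in SAP 9. The interaction is needed because a main effect cancels from the change contrast. Fix the functional form in advance, since unrestricted entry may make the variable skewed. Days from surgery to randomisation can be derived from SAP 8.2 and 8.3 as (surgery to evaluation) + (evaluation to discharge) − (randomisation to discharge). Do not adjust for PT duration, which arises after randomisation.
2. Keep the discharge-anchored visits as primary, and say plainly that the estimand is defined relative to discharge. Add one sensitivity model that uses actual days since randomisation at each assessment and reports the group difference at a common day. With item 1 in the model, this also carries time since surgery.
3. Reconcile the fixed measurement times of SAP 7.4 with the variable discharge day of SAP 6.4.

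The cost is a few sentences in the SAP, one extra model, and a few degrees of freedom (three parameters in the three-visit model: one main effect and two interaction terms). No new data are needed. The additions should be specified before the final analysis is run.

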7.1 Timing of Analyses

Final analyses will be performed when data collection is completed. In particular, the final analyses will be performed when all enrolled study subjects have completed the 12 month follow up or dropped out prior to the 12 month follow up. The final analysis will be performed on data transferred to a file from RedCap, having been documented as meeting the cleaning and approval requirements after the finalization and approval of this SAP document. In particular data cleaning will involve checking physical documents for errors/discrepancies, ensuring all responses are correctly entered into REDCap, and then performing a quality check to ensure answers were entered accurately. For the ActiGraph, we will ensure data was recorded at 60Hz, that data fell within the expected wear time range, and that included participants met our wear time criteria of at least 4 days and at least 10 hours on those days.

7.2 Analysis Populations

(ICH E3; 9.7.1, 11.4.2.5. ICH E9; 5.2)

7.2.1 Full Analysis Sample (Intention to Treat)

- All subjects who were randomized
- The ActiGraph monitor was worn for > 4 days of 10 hours of wear time each time point (baseline, discharge, and 6 months).
- This sample will be the primary efficacy sample

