7.4 Missing Data

(ICH E3; 9.7.1, 11.4.2.2. ICH E9;5.3. EMA Guideline on Missing Data in Confirmatory Clinical Trials)

Missing data will be given careful attention in the analysis. In this RCT we have two treatment arms and four fixed times tied to the recovery process for measurements. It is anticipated that drop-outs from the study will be limited because all have elected to undergo knee replacement surgery and would be working toward recovery. However, it is possible that participants may not attend all follow-ups. Drastically fewer participants in the final analysis would affect study sensitivity and excessive missed follow-ups would potentially bias model parameter estimates. Under the assumption of limited data that is missing completely at random (MCAR) or missing at random (MAR), the mixed-effect model using restricted maximum likelihood estimation is a full information approach and leads to unbiased model parameter estimates. Selection between two common covariance structures, Toeplitz and AR(1), will be accomplished using the Akaike Information Criterion (AIC).

In the event that assumptions are not met regarding missing value frequency, MAR, or MCAR and missing values are occurring with higher frequency or are truly missing not at random (MNAR), the analysis may be biased. To test the missingness assumptions, missing data will first be summarized by group, time, each design cell, and each of the three covariates, age, sex and body mass index in an effort to graphically or tabularly detect patterns in the variation of missingness. More formally, missing/nonmissing will be taken as a dichotomous outcome in a logistic regression for continuous covariates and will be compared with between and within factors and sex using chi-square tests. Significant logistic regression that will be identified and reported and whose impact on the analysis will be explained if possible.

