8.3 Treatment Compliance

Characteristic [mean ± SD or n (%)]	All n=	Intervention n =	Control n =
Days Randomization to Discharge			
Days Eval to Discharge			

Characteristic [mean ± SD or n (%)]	Intervention n =
Percent of days in PT in the study that the Fitbit was checked (recorded or checked on HEP):	
Percent of weeks in PT in the study that a step goal was recorded:	

9 Efficacy Analyses

The primary and secondary outcomes will be summarized stratified by treatment group at each study timepoint (baseline, discharge, 6-month, 12-month). Our primary analysis will use an intention-to-treat (ITT) analysis that includes all participants who wore the monitor for \geq 4 days at baseline. The statistical model underlying the analysis a mixed-effects model to examine the main and interaction effects of *group* (Intervention vs. Control) and *time* (BL, DC, 6M, and 12M) on MVPA (minutes/day). We will adjust this model for age, sex, and body mass index. The null hypothesis is that there is no difference in change in MVPA in the intervention group compared to the control group. The alternative hypothesis is that there is a difference between groups. The nature of the hypothesis is confirmatory as this study has been powered to detect a difference should one exist. The mixed-effect model will be used to calculate the mean and 95% Confidence Interval time in MVPA at each study time point. We will also calculate difference in means and 95% Confidence Intervals between the intervention and control group at each study time point. We will also calculate 2-sided p-values to determine statistical significance of differences between groups by time in MVPA.

• Methods and assumptions for handling longitudinal data or missing data.

Mixed-effect modeling will be used to estimate MVPA over time. The mixed-effect model using restricted maximum likelihood estimation is a full information approach and leads to unbiased model parameter estimates in the presence of MCAR or MAR missingness. Selection between two common covariance structures, Toeplitz and AR(1), will be accomplished using the Akaike Information Criterion (AIC).

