9.1 Primary Efficacy Analysis

The primary endpoint of our study is to examine the efficacy of a Physical Therapistadministered physical activity intervention and standardized outpatient PT to increase MVPA over 6 months after discharge from outpatient PT compared to a control group that received standardized outpatient PT.

The statistical model underlying this analysis is a mixed-effects model to examine the main and interaction effects of *group* (Intervention vs. Control) and *time* (BL, DC, and 6M) on MVPA (minutes/day). We will adjust this model for age, sex, and body mass index.

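### SAP 7.2.1 and Section 9 define the primary intention-to-treat sample differently; followed literally, 7.2.1 makes the 6-month primary analysis a completers' analysis

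*SAP*

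**What the plan says.** SAP 7.2.1 (Full Analysis Sample) starts from all randomised subjects and then adds a wear condition: "The ActiGraph monitor was worn for > 4 days of 10 hours of wear time each time point (baseline, discharge, and 6 months"). It continues: "This sample will be the primary efficacy sample".

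SAP Section 9 describes the primary analysis as an "intention-to-treat (ITT) analysis that includes all participants who wore the monitor for" at least 4 days at baseline. No later visit is mentioned.

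SAP 9.1 fits the primary mixed model to baseline, discharge and 6 months, the same three visits that 7.2.1 requires. Section 9 frames the hypothesis in terms of change: "The null hypothesis is that there is no difference in change in MVPA in the intervention group compared to the control group".

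On missing data, SAP 7.4 expects limited drop-out but accepts that "it is possible that participants may not attend all follow-ups". Both 7.4 and Section 9 rely on a REML mixed model being unbiased when data are missing completely at random or at random. 7.4 also plans tabulations of missingness, logistic regression and chi-square tests, without saying on which sample, and it names no alternative analysis.

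The closing paragraph of SAP 7.2.2 defers the exact process of assigning people to samples to a later document, to be written before unblinding.

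**The concern.** Two paragraphs of one SAP version define the primary population of an analysis that Section 9 calls confirmatory, and they do not select the same participants. The primary result therefore depends on which paragraph the analyst follows.

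The stricter rule also undoes the rest of the plan. If valid wear at all three modelled visits is needed to enter, the 9.1 model has no missing outcomes. Anyone with a valid baseline and only one valid follow-up visit is discarded, although a mixed model could use them. Entry is then decided by behaviour after randomisation, under an intention-to-treat label. Participants and treating therapists know the assignment (SAP 6.1), and the 6-month monitor has to be worn at home and mailed back (Protocol, thank you notes and phone calls). Baseline wear is collected before randomisation (Protocol, participant recruitment), so the Section 9 condition carries no such risk.

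The only other population named for the primary endpoint is the per-protocol sample (SAP 7.2.2 and 9.2.1). It also requires 12-month wear and no drop-out, so it is more selected still and cannot act as a check.

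**Working it through.** **1. The two rules side by side**

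| | SAP 7.2.1 | SAP Section 9 |
|---|---|---|
| Label | Intention to treat, primary efficacy sample | Intention to treat, primary analysis |
| Valid wear needed at | baseline, discharge, 6 months | baseline |
| Missing visits possible in the 9.1 model | none | discharge, 6 months or both |
| Condition measured | partly after randomisation | before randomisation |

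**2. Inputs for the illustration.** N = 120 comes from SAP Section 7, which gives no effect size, SD, power or drop-out rate, so there is no stated calculation to reproduce. Two-sided testing is from Section 9. Everything else is assumed: independent probability *p* of valid wear per visit, equal arms, alpha 0.05, and a true difference of 0.5 SD.

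**3. Head counts**

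| | formula | p = 0.95 | p = 0.90 | p = 0.85 |
|---|---|---|---|---|
| Admitted, Section 9 | 120p | 114 | 108 | 102 |
| Baseline and 6 months valid | 120p² | 108.3 | 97.2 | 86.7 |
| Admitted, 7.2.1 | 120p³ | 102.9 | 87.5 | 73.7 |
| Valid baseline, exactly one follow-up | 120p·2p(1−p) | 10.8 | 19.4 | 26.0 |

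The last row is the group that 7.2.1 throws away although they have usable follow-up. By symmetry, half of them have the 6-month value.

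**4. Power.** This is a simple two-group comparison by noncentral t, not the mixed model. It compares those with baseline and 6 months valid against those with all three visits valid. For change from baseline, d = 0.5/√(2(1−ρ)), where ρ is the correlation between baseline and 6 months; at ρ = 0.50 this equals the 6-month comparison.

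| | p = 0.95 | p = 0.90 | p = 0.85 |
|---|---|---|---|
| 6-month difference, or change at ρ = 0.50 | 73.2 → 70.9% | 68.4 → 63.8% | 63.4 → 56.3% |
| Change, ρ = 0.35 | 61.8 → 59.6% | 57.1 → 52.7% | 52.3 → 45.9% |
| Change, ρ = 0.65 | 86.9 → 85.1% | 83.0 → 78.9% | 78.5 → 71.6% |

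The loss is about 2 to 7 percentage points. It is zero if the same people miss both follow-up visits.

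**5. Bias under a true null.** Take unit-variance normal outcomes with discharge fully observed, and logit P(6 months missing) = a − b·(discharge value). Let b = 0 in control and 0.5 or 1.0 in intervention, so that only in the intervention arm does low discharge activity predict missing wear. Let m be the mean discharge value, in SD, among intervention participants with 6 months observed. Among completers:

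- bias in the 6-month difference = r(discharge, 6 months) × m
- bias in the change from baseline to 6 months = [r(discharge, 6 months) − r(baseline, discharge)] × m

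| a, b | missing, control / intervention | m | change bias, at most | 6-month bias |
|---|---|---|---|---|
| −2.2, 0.5 | 10% / 11% | 0.053 | ±0.016 | 0.019 to 0.034 |
| −2.2, 1.0 | 10% / 13% | 0.119 | ±0.036 | 0.042 to 0.077 |
| −1.0, 0.5 | 27% / 28% | 0.133 | ±0.040 | 0.047 to 0.087 |
| −1.0, 1.0 | 27% / 30% | 0.255 | ±0.077 | 0.089 to 0.166 |

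Correlations run from 0.35 to 0.65, so the two can differ by at most 0.30. Change bias is zero when they are equal. Both biases are about zero when the missingness pattern is the same in both arms. A missing-at-random analysis of everyone gives about zero here, by construction of the scenario.

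**6. A second mechanism.** In a simulation with a true effect of 0.50 SD and equal correlations of 0.5 or 0.7, loss depended on the change from baseline to discharge in the intervention arm only (10 to 30% loss in control). Completers gave an estimated change of 0.53 to 0.64, and likelihood estimation on all participants gave 0.50. With the same dependence in both arms, both methods gave 0.50.

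**The case against.** The strongest reply is that the bullet in 7.2.1 was meant as a visit-level validity rule, not an entry condition. There is real support for this. The bullet before it admits all randomised subjects. Completing physical therapy and not dropping out are listed only for the per-protocol sample. The REML and missing-at-random text makes sense only with incomplete participants in the model. Section 8 allows for missing observations in table totals, and 6.4 keeps out-of-window data in the primary analyses. Section 9 probably reflects the intent.

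The text still does not say so. The bullet sits in a population definition, and its near-twin in 7.2.2 is plainly a subject-level criterion. A visit-validity rule would also have had to cover 12 months, because Mock Tables 1 and 2 report 12-month values for the intention-to-treat sample. The data-cleaning sentence in 7.1 refers to included participants meeting the wear rule but names no visits, so it helps neither side.

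The promise to document sample assignment before unblinding, and the blinded final statistician (7.5.4), limit a result-driven choice between the rules. They do not make the choice. Gift cards for wear, reminders to all participants, and continued follow-up after stopping the intervention should reduce missingness, but they too leave the question open.

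Two cautions on the numbers stand. The largest change bias needs about 27 to 30% missing, the steepest slope in one arm only, and correlations at opposite extremes. Change from baseline to 6 months is also only one contrast within the group-by-time test; Section 9 does not name it as the sole one.

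**Conclusion.** The concern holds and should be corrected before analysis. Its weight rests on the contradiction over who is in the primary analysis, which can be read directly from 7.2.1 and Section 9, and not on the illustrative figures. If 7.2.1 is followed as written, the 6-month primary analysis is a completers' analysis under an intention-to-treat label. The point does not extend to the 12-month analysis in the same form, since 7.2.1 does not require 12-month wear.

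The size is uncertain because the documents give no attrition rate. Under independent valid wear of 85 to 95% per visit, about 11 to 26 people with usable follow-up would be dropped. Bias is a risk and not a certainty: it needs missingness that depends on earlier activity differently in the two arms. In the first scenario it lies between about −0.08 and +0.08 SD for change, and about +0.02 to +0.17 SD for the 6-month difference. The second one-arm mechanism overstated change by 0.03 to 0.14 SD.

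**What to change.** Rewrite 7.2.1 to agree with Section 9:

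- The primary sample is all randomised participants with a valid baseline, analysed as assigned. Remove discharge and 6 months from the entry condition.
- A later visit that fails the wear rule is set to missing, and the participant stays in the mixed model.
- Use one wear rule throughout: the 7.1 rule of at least 4 days with at least 10 hours on each. (The sign in 7.2.1 and 7.2.2 may be a greater-or-equal sign damaged in the PDF; the finding does not depend on it.)
- Say that the missingness summaries in 7.4 are run on this sample.
- Label any all-visits-valid set a sensitivity analysis.

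The cost is SAP wording only, with no new data and the same model. The baseline rule is already in Section 9; the 10-hour condition there and the set-to-missing statement are small additions.
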